7.3 TREATMENT COMPLIANCE

Treatment compliance will not be analyzed as a specific endpoint (cf. [Section 5.4.2](#)). Any deviations from complete intake will be addressed in the RPM (cf. [Section 6.2](#)) and described in the CTR.

7.4 PRIMARY ENDPOINTS

7.4.1 Primary analysis of the primary endpoint

The primary endpoints of Part 1 will be analysed descriptively (cf. Section 7.3.1 of the CTP).

The analysis is performed according to BI standards ([4](#)) and will be based on the PKS.

Exclusion of PK parameters (applies to Part 1 and Part 2)

The ADS ADPP contains column variables APEXC and APEXCO indicating inclusion/exclusion (APEXC) of a PK parameter and an analysis flag comment (APEXCO). All analyses based on the PKS are based on PK parameter values which are not flagged for exclusion, i.e. with APEXC equal to "Included".

Exclusion of plasma/urine concentrations (applies to Part 1 and Part 2)

The ADS ADPC (PK concentrations per time-point or per time-interval) contains column variables ACEXC or ACEXCO indicating inclusion/exclusion (ACEXC) of a concentration and an analysis flag comment (ACEXCO).

Exclusion of a concentration depends on the analysis flag comment ACEXCO. For example, if ACEXCO is set to "ALL CALC", the value will be excluded for all types of analyses based on concentrations. If ACEXCO is set to "DESC STATS" the value will be excluded from descriptive evaluations per planned time point/time interval. If ACEXCO contains the addition "TIME VIOLATION" or "TIME DEVIATION", the value can be used for further analyses based on actual times. If ACEXCO is set to "HALF LIFE", the value will be excluded from half-life calculation only; the value is included for all other analyses. Excluded concentration itself will be listed in the CTR associated with an appropriate flag.

Further details are given in "Noncompartmental Pharmacokinetic / Pharmacodynamic Analyses of Clinical Studies" (4) and "Description of Analytical Transfer Files and PK/PD Data Files" (5).

7.4.2 Sensitivity analysis, subgroup analysis, exploratory analysis of the primary endpoints

Not applicable.

7.5 SECONDARY ENDPOINTS

[figure not shown]
7.5.1 Key secondary endpoints

This section is not applicable as no key secondary endpoint has been specified in the CTP.

7.5.2 Secondary endpoints

Secondary PK endpoints of both parts will be assessed descriptively. This will be based on the PKS. The analysis of PK parameters is performed according to BI standards (4).

See [Section 7.4.1](#) of this TSAP for details regarding exclusion of PK parameters and plasma concentrations.

7.7 EXTENT OF EXPOSURE

For Part 1 treatment exposure will only be listed by means of the date and time of drug administration

For Part 2 descriptive statistics are planned for this section of the report.

7.8 SAFETY ANALYSIS

All safety analyses will be performed on the TS.

7.8.1 Adverse Events

AEs will be coded with the most recent version of MedDRA.

The analyses of AEs will be descriptive in nature. All analyses of AEs will be based on the number of subjects with AEs and not on the number of AEs.

For further details on summarization of AE data, please refer to "Analysis and Presentation of Adverse Event Data from Clinical Trials" ([7](#)) and "Handling of missing and incomplete AE dates" ([3](#)).

The analysis of AEs will be based on the concept of treatment emergent AEs. That means that all AEs will be assigned to screening, on-treatment or follow-up phases as defined in [Section 6.1](#). AEs will be analysed based on actual treatments, as defined in [Table 6.1: 1](#) and [Table 6.1: 2](#).

An overall summary of AEs will be presented. This overall summary will comprise summary statistics for the class of AESIs.

CTP Section 5.2.6.1.3: *The following are considered as AESIs:*

- Hepatic injury
A hepatic injury is defined by the following alterations of hepatic laboratory parameters:
 - *An elevation of AST (aspartate transaminase) and/or ALT (alanine transaminase) ≥ 3 -fold ULN combined with an elevation of total bilirubin ≥ 2 -fold ULN measured in the same blood sample, or*
 - *Aminotransferase (ALT, and/or AST) elevations ≥ 10 fold ULN*

The investigator had to classify on the eCRF whether an observed AE was an AESI or not.

According to ICH E3 (8) in addition to deaths and SAEs, "other significant" AEs need to be listed in the CTR. These will be any non-serious adverse event that led to an action taken with study drug (e.g. discontinuation or dose reduced or interrupted).

The frequency of subjects with AEs will be summarised by treatment, primary SOC and preferred term. AEs which were considered by the investigator to be drug related will be summarised separately. AEs will also be summarized by maximum intensity. Separate tables will be provided for subjects with SAEs and subjects with AESIs.

The SOCs will be sorted by total frequency; preferred terms will be sorted by total frequency (within SOC).

For disclosure of AE data on ClinicalTrials.gov, the frequency of subjects with non-serious AEs occurring with an incidence of greater than 5 % (in preferred terms) will be summarised by treatment, primary SOC and preferred term. The frequency of subjects with SAEs will also be summarised.

For disclosure of AE data in the EudraCT register, the frequency of AEs, the frequency of non-serious AEs with an incidence of greater than 5 % (in preferred terms) and the frequency of SAEs will be summarised.

For support of lay summaries, the frequency of subjects with drug-related SAEs will be summarized by treatment, primary SOC and preferred term.

If the subject reports headaches during the treatment period further information about the duration of headache, location, characteristics, and signs and symptoms were recorded. These data will be summarized with descriptive statistics. Headache episodes with onset during screening and Follow-up phase will be listed only.

7.8.2 **Laboratory data**

The analyses of laboratory data will be descriptive in nature and will be based on BI standards "Display and Analysis of Laboratory Data" (9).

Analyses will be based on normalised values, which means transforming to a standard unit and a standard reference range. The original values will be analysed if the transformation into standard unit is not possible for a parameter.

Descriptive statistics of laboratory values over time and for the difference from baseline (see [Section 6.7](#)) will be provided for the on-treatment phase. Frequency tables of changes between baseline and last value on treatment with respect to the reference range will be presented. Qualitative urinalysis results will be listed only.

CTP Section 7.3.4: *Values outside the reference range as well as values defined as possibly clinically significant will be highlighted in the listings.*

Unscheduled measurements of laboratory data will be assumed to be repeat measurements of the most recent scheduled measurement (e.g. for follow-up or confirmation of a particular value). Therefore, unscheduled measurements will be assigned to the planned time point of the previous scheduled measurement. Descriptive statistics will be calculated by planned time point based on the worst value of the subject at that planned time point (or assigned to that planned time point).

Possibly clinically significant abnormal laboratory values are only those identified either in the Investigator's comments or at the RPM at the latest. It is the Investigator's responsibility to decide whether a lab value is clinically significant abnormal or not. Standard or project-specific rules for flagging clinically significant values in an automated manner will not be applied in this study.

Clinically relevant findings in laboratory data will be reported as baseline conditions (prior to first administration of study treatment) or as AEs (after first administration of study treatment) if judged clinically relevant by the investigator, and will be analyzed as such.

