14. Subjects will collect a pre-dose faeces sample at home in specific containers provided by [REDACTED]
15. Confirmation of fitness includes physical and neurological examination, vital signs, ECG, suicidality assessment (C-SSRS) only at Day 15 and EOT, recordings of AEs and concomitant therapies as well as evaluation of safety laboratory assessed on Day 8.
16. At this time point, only a sample for haematocrit measurement is taken.
17. PCR testing for SARS-CoV-2 will be performed at admission on Day – 1, on Day 2, at each admission to the trial site for the 24-h visits and at EOT.

Proprietary confidential information © 2020 Boehringer Ingelheim International GmbH or one or more of its affiliated companies

Flow Chart: Part 2 (Multiple dose)

Visit	Day	Planned time (relative to drug administration) [h:min]	Approximate clock time of actual day [h:min]	Event and comment	Safety laboratory	PK _{plasma} ^{2,9}	PK _{urine} ⁵	12-lead ECG	Vital signs (BP, PR)	Questioning for AEs & concomitant medication
1	-21 to -2			Screening (SCR) ¹	A			x	x	x
2	-1	-21:00	11:00	Admission to trial site	B ^{10, 11}					x
	1	-2:00	06:00			x ³	x ³	x ³	x ³	
		-0:30	07:30	Standard continental breakfast						
		0:00	08:00	Drug administration						
		0:30	08:30			x				
		1:00	09:00			x				
		2:00	10:00			x				
		4:00	12:00	Lunch ⁶		x				
		5:00	13:00			x				
		6:00	14:00			x				
		7:00	15:00			x				
		8:00	16:00			x				
		10:00	18:00	Dinner ⁶		x				
		12:00	20:00	Snack ⁶		x				
		14:00	22:00			x				
	2	24:00	08:00	Drug administration ¹²	x ¹¹	x ³	x ³			
	3	48:00	08:00	Drug administration ¹²						
	4	72:00	08:00	Drug administration ¹²						
	5	96:00	08:00	Drug administration ¹²						
	6	120:00	08:00	Drug administration ¹²						
	7	144:00	08:00	Drug administration ¹²	B ⁸	x ³	x ³	x ³	x ³	
		144:30	08:30			x				
		145:00	09:00			x				
		146:00	10:00			x				
		148:00	12:00	Lunch ⁶		x				
		149:00	13:00			x				
		150:00	14:00			x				
		151:00	15:00			x				
		152:00	16:00			x				
		154:00	18:00	Dinner ⁶		x				
		156:00	20:00	Snack ⁶		x				
		158:00	22:00			x				
	8	168:00	08:00	Drug administration ¹²		x ³				
	9	192:00	08:00	Drug administration ¹²		x ³	x ³			
	10	216:00	08:00	Drug administration ¹²						
	11	240:00	08:00	Drug administration ¹²		x ³	x ³			
	12	264:00	08:00	Drug administration ¹²						
	13	288:00	08:00	Drug administration ¹²						
	14	312:00	08:00	Drug administration ¹²	B ⁸	x ³	x ³	x ³	x ³	
		312:30	08:30			x				
		313:00	09:00			x				
		314:00	10:00			x				

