5.2.6.1.4 Adverse events of special interest

The term adverse events of special interest (AESI) relates to any specific AE that has been identified at the project level as being of particular concern for prospective safety monitoring and safety assessment within this trial, e.g. the potential for AEs based on knowledge from other compounds in the same class. AESIs need to be reported to the sponsor’s Pharmacovigilance Department within the same timeframe that applies to SAEs, please see Section [5.2.6.2.2](#).

The following are considered as AESIs:

- Hepatic injury

A hepatic injury is defined by the following alterations of hepatic laboratory parameters:

- o An elevation of AST (aspartate transaminase) and/or ALT (alanine transaminase) ≥ 3 -fold ULN combined with an elevation of total bilirubin ≥ 2 -fold ULN measured in the same blood sample, or
- o Aminotransferase (ALT, and/or AST) elevations ≥ 10 fold ULN

These lab findings constitute a hepatic injury alert and the subjects showing these lab abnormalities need to be followed up according to the 'DILI checklist' provided in the ISF. In case of clinical symptoms of hepatic injury (icterus, unexplained encephalopathy, unexplained coagulopathy, right upper quadrant abdominal pain, etc.) without lab results (ALT, AST, total bilirubin) available, the Investigator should make sure that these parameters are analysed, if necessary in an unscheduled blood test. Should the results meet the criteria of hepatic injury alert, the procedures described in the DILI checklist should be followed.

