7.3.4 Safety analyses

Safety will be analysed based on the assessments described in Section [2.2.2.2](#). All treated subjects (TS, refer to Section [7.2](#)) will be included in the safety analysis. Safety analyses will be descriptive in nature and based on BI standards. No hypothesis testing is planned.

For all analyses, the treatment actually administered (= treatment at onset) to the subject will be used (any deviations from the randomised treatment will be discussed in the minutes of the Report Planning Meeting).

Proprietary confidential information © 2020 Boehringer Ingelheim International GmbH or one or more of its affiliated companies

Treatments will be compared in a descriptive way. Tabulations of frequencies/proportions will be used to evaluate categorical (qualitative) data, and tabulations of descriptive statistics will be used to analyse continuous (quantitative) data.

Measurements (such as ECG, vital signs, or laboratory parameters) or AEs will be assigned to treatments (see Section [4.1](#)) based on the actual treatment at the planned time of the measurement or on the recorded time of AE onset (concept of treatment emergent AEs). Therefore, measurements planned or AEs recorded prior to first intake of trial medication will be assigned to the screening period, those between first trial medication intake and end of REP (see Section [1.2.2](#)) will be assigned to the treatment period. Events occurring after the REP but prior to next intake or end of trial termination date will be assigned to 'follow-up'. In case of two or more treatments, the follow-up will be summarized according to the previous treatment. These assignments including the corresponding time intervals will be defined in detail in the TSAP. Note that AEs occurring after the last per protocol contact but entered before final database lock will be reported to Pharmacovigilance only and will not be captured in the trial database.

Additionally, further treatment intervals (analysing treatments) may be defined in the TSAP in order to provide summary statistics for time intervals, such as combined treatments, on-treatment totals, or periods without treatment effects (such as screening and follow-up intervals).

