7.7 DETERMINATION OF SAMPLE SIZE

For this exploratory trial, no prospective calculations of statistical precision or power have been made. The planned sample size of 8 evaluable subjects per study part, 16 subjects in total, has been selected for practical reasons and is judged as being adequate to get reliable results regarding the trial objectives.

8. INFORMED CONSENT, TRIAL RECORDS, DATA PROTECTION, PUBLICATION POLICY, AND ADMINISTRATIVE STRUCTURE

The trial will be carried out in compliance with the protocol, the ethical principles laid down in the Declaration of Helsinki, in accordance with the ICH Harmonized Guideline for Good Clinical Practice (GCP), relevant BI Standard Operating Procedures (SOPs), and other relevant regulations. Investigators and site staff must adhere to these principles.

Standard medical care (prophylactic, diagnostic, and therapeutic procedures) remains the responsibility of the subject's treating physician.

The investigator will inform the sponsor immediately of any urgent safety measures taken to protect the trial subjects against any immediate hazard, as well as of any serious breaches of the protocol or of ICH GCP.

The Boehringer Ingelheim transparency and publication policy can be found on the following web page: trials.boehringer-ingelheim.com. The rights of the investigator and of the sponsor with regard to publication of the results of this trial are described in the investigator contract. As a general rule, no trial results should be published prior to archiving of the CTR.

The terms and conditions of the insurance coverage are made available to the investigator and the subjects, and are stored in the ISF.

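### SAP 7.8.2 carries an unscheduled laboratory sample back across the first dose, so an early post-dose full-panel value is labelled Day -1 and has no row in the on-treatment statistics by time point

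*SAP*

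**What the plan says.** SAP 7.8.2 states the assumption: "Unscheduled measurements of laboratory data will be assumed to be repeat measurements of the most recent scheduled measurement". The consequence is that "unscheduled measurements will be assigned to the planned time point of the previous scheduled measurement". The summary rule is then: "Descriptive statistics will be calculated by planned time point based on the worst value of the subject at that planned time point", and values assigned to that time point count as well. The laboratory statistics over time and for change from baseline "will be provided for the on-treatment phase". A shift table compares baseline with the last on-treatment value.

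Three other places bear on this:

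- Protocol 7.3.4 allocates measurements to phases by planned time: "measurements planned or AEs recorded prior to first intake of trial medication will be assigned to the screening period". It leaves the detailed intervals to the SAP.
- SAP Tables 6.1:1 and 6.1:2 bound the phases by date and time of drug administration, with a 14-day residual effect period (REP) after the (last) dose.
- SAP 6.7 defines baseline as the last non-missing value determined before the first dose.

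In the Part 1 Flow Chart, the laboratory entries on Day 1 and at 24 h are not full panels. Footnote 16 says: "At this time point, only a sample for haematocrit measurement is taken". The 24 h entry also carries a PCR test. In Part 2 the Day 2 entry is the PCR test only.

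**The concern.** Treating an unscheduled sample as a repeat is sensible when it is drawn soon after a scheduled one to confirm a result. It is not sensible when the two are separated by the first dose. A sample drawn on Day 3 because a subject feels unwell is not a repeat of the Day -1 admission panel, yet the rule gives it that label.

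The protocol foresees such samples. For clinical symptoms of hepatic injury without laboratory results, section 5.2.6.1.4 asks that the liver parameters be analysed, "if necessary in an unscheduled blood test". Unscheduled samples are thus more likely than others to be abnormal, and the rule places the early ones before exposure. With 8 subjects per part, one subject is 1/8 = 12.5% of a table, so one mislabelled value can change what a row shows.

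**Working it through.** The trial is descriptive and protocol 7.7 says that "no prospective calculations of statistical precision or power have been made", so there is no planned figure to reproduce. The check applies the SAP 7.8.2 rule to the Flow Chart times.

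**Inputs (hours from first dose)**

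| | Part 1 | Part 2 |
|---|---|---|
| Pre-dose full panel (set B) | Day -1 (-21 h) | Day -1 (-21 h) |
| Post-dose full panels (set B) | 168 (Day 8), 336 (Day 15) | 144 (Day 7), 312, 480, 624 (Day 27) |
| Other laboratory entries up to Day 27 | haematocrit at -2, 1, 4, 8, 24 h; PCR at 24 h | PCR at 24 h |
| Last dose | 0 h | 480 h |
| End of on-treatment phase (exclusive) | 0 + 14 × 24 = 336 h | 480 + 14 × 24 = 816 h |

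**Step 1: assigned time point.** Assigned time = latest scheduled time for that parameter at or before the draw. For any set B parameter other than Part 1 haematocrit and the PCR, every draw from first dose up to the first post-dose panel is assigned to -21 h, that is, Day -1.

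**Step 2: share of the on-treatment phase exposed.**

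- Part 1: 168 / 336 = 50%
- Part 2: 144 / 816 = 17.6%
- Part 1 haematocrit: only draws in the first hour go to a pre-dose point (-2 h), so 1 / 336 = 0.3%

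**Step 3: effect on the tables by time point.** A value labelled Day -1 sits at no on-treatment planned time, so it is in no on-treatment row. If a Day -1 row is produced, the worst-value rule could put a post-dose value in it. That would conflict with SAP 6.7, although the baseline used for change scores stays pre-dose.

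**Step 4: phase, under two readings.**

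- *Planned time governs (protocol 7.3.4).* Day -1 precedes first intake, so the value falls in screening. In the other direction, Part 2 has no panel between Day 27 (624 h) and Day 62. A sample drawn from 816 h (Day 35) up to Day 62 belongs to follow-up but is assigned to Day 27, an on-treatment point, where it can replace the true Day 27 value if it is worse. Subjects are questioned for AEs at seven ambulatory visits between Day 37 and Day 58, so such a sample is plausible.
- *Actual time governs (a possible reading of Tables 6.1:1 and 6.1:2).* The early sample is on-treatment and the late one is in follow-up, but their planned-time labels remain Day -1 and Day 27. Step 3 is unchanged.

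**Step 5: shift table.** It uses the last on-treatment value. Part 1 has the Day 8 panel; Part 2 has Days 7, 14, 21 and 27. An early sample is normally superseded whatever label it carries, so the rule matters only for a subject with no later on-treatment panel. Part 1 has little reserve: its Day 15 panel is planned at 336 h, the exclusive end of the phase, so by planned time Day 8 is the only on-treatment full panel.

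**The case against.** A reader might infer that a drug-related abnormality in the first week would disappear from the safety evaluation, or from the shift table. The documents do not support that. SAP section 7 lists all individual values, and SAP 7.8.2 highlights those outside the reference range. Findings after first dose that the investigator judges clinically relevant are analysed as AEs, and protocol 7.3.4 assigns AEs by onset time. Hepatic injury is an AESI with its own table. The shift table is largely unaffected, as shown in Step 5. These objections stand and limit the consequence to the descriptive rows by time point.

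It can also be said that the move to screening is not certain. Protocol 7.3.4 defers detail to the SAP, whose tables use dates and times. That stands too: the screening label and the late Part 2 carry-back hold under one of two readings. It does not rescue the time-point label, which is wrong under both.

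The vital-signs rule in SAP 7.8.3 might be offered as the model because of its 20-minute limit. It avoids a wrong label, but it also leaves later values out of the statistics, so it is no precedent for keeping them.

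Finally, the ADS Plan and the sponsor's laboratory standard, to which the SAP refers, are not among the documents and may handle the boundary. The SAP text should still not state a rule that they would have to override.

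**Conclusion.** The point holds as a defect in a stated rule, with modest consequences. For all set B parameters except Part 1 haematocrit and the PCR, an unscheduled post-dose sample drawn before the first post-dose panel is labelled Day -1 and has no row in the on-treatment statistics by time point. The window is the first 168 of 336 on-treatment hours in Part 1 (50%) and the first 144 of 816 in Part 2 (17.6%). These are lengths of time at risk, not shares of data affected; the documents give no expected number of unscheduled samples.

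The result assumes that the previous scheduled measurement is identified per parameter. The idea of a repeat implies this, but the SAP does not say it. If any laboratory entry counted, the pre-dose window would shrink to 1 / 336 = 0.3% in Part 1 and 24 / 816 = 2.9% in Part 2, with full-panel values then placed at haematocrit-only or PCR-only time points.

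Allocation to screening, and counting a post-REP Part 2 sample at Day 27 as on-treatment, additionally require that planned time decides the phase. Protocol 7.3.4 and SAP Tables 6.1:1 and 6.1:2 need to be reconciled on that.

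**What to change.** In SAP 7.8.2, state three things:

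1. The analysis phase of an unscheduled laboratory sample follows its actual draw date and time, using Tables 6.1:1 and 6.1:2. This also settles the conflict with the planned-time wording in protocol 7.3.4.
2. Such a sample is treated as a repeat only of a scheduled sample of the same parameter in the same phase. A Part 2 sample drawn after the REP and before Day 62 then stays in follow-up and cannot alter the Day 27 row.
3. A post-dose sample drawn before the first post-dose panel is shown in a separate 'unscheduled, on treatment' row.

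The early sample should not be moved forward to Day 7 or Day 8 instead. That misdates it again and, under the worst-value rule, could displace the true panel result.

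The cost is a short addition to SAP 7.8.2 and a matching derivation in the ADS Plan. No new data are needed. The drawback is an occasional extra table row, often with a single subject in it.
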